### 5.3.5 Dose Modifications

Inpatient dose interruptions and/or reductions will be permitted provided that study discontinuation criteria have not been met (please see Section 10).

- Patients experiencing treatment-related seizure of any grade will have study drug permanently discontinued.

- For patients experiencing Grades 1-2 treatment-related adverse events, short treatment breaks can be instituted as per the discretion of the Investigator until the severity of the toxicity decreases to Grade 1 or returns to baseline. If toxicity recurs, dose reductions to the next lower dose level will be allowed as per the discretion of the Investigator.
- For patients experiencing Grade  $\geq 3$  treatment-related adverse events other than seizure, study drug should be held until the severity of the toxicity decreases to Grade 1 or returns to baseline. If toxicity recurs at Grade 3 or higher, the dose of apalutamide should be reduced to the next lower dose level. A maximum of 2 dose level reductions will be allowed (Table 1).
- Any patient requiring > 28 days delay in treatment due to AEs may meet one of the criteria for study treatment discontinuation (see Section 10), which must be discussed with Sponsor.

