## 10. END OF TREATMENT

A patient may be discontinued from study treatment at any time if the patient, the Investigator, or the Sponsor feels that it is not in the patient's best interest to continue on study. If a patient's study treatment must be discontinued, this will not result in automatic withdrawal of the patient from the study.

The following is a list of possible reasons for early discontinuation of study treatment:

- Disease progression (*patients should be highly encouraged to stay on study treatment until there is BICR-confirmed radiographic progression; treatment decisions should not be based on PSA alone*)
- Any episode of seizure
- Any other adverse event that cannot be adequately managed with dose modifications, including dose interruption for  $\geq 28$  days may require study drug discontinuation, which must be discussed with the Sponsor.
- Protocol violation requiring discontinuation of study treatment
- Patient is not compliant with study procedures
- Lost to follow-up
- Patient withdrawal of consent

- Sponsor request for early termination of study

All patients discontinuing study treatment will enter the Long-term Follow-up Phase and will be followed for the development of symptomatic progression and initiation of subsequent anti-cancer therapies every 4 months until death, loss of follow-up, or withdrawal of consent, whichever comes first.

If a patient is lost to follow-up, every reasonable effort must be made by the study site personnel to contact the patient and determine the reason for discontinuation/withdrawal. The measures taken to follow up must be documented.

When a subject withdraws before completing the study, the reason for withdrawal is to be documented in the CRF and in the source document. Study drug assigned to the withdrawn subject may not be assigned to another subject. Subjects who withdraw will not be replaced.

Data to be collected for the end of treatment visit are described in Section 8.7. Patients will be followed for at least 28 days after the last dose of study drug. If a patient is withdrawn from treatment due to an adverse event, the patient will be followed until the adverse event has resolved or stabilized as per Section 9.2.

For information on subsequent therapy with abiraterone acetate see Section 8.10

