### **15.6 END OF TRIAL IN ALL PARTICIPATING COUNTRIES**

Patients will remain on study treatment until BICR-confirmed disease progression, development of unacceptable toxicity, or withdrawal of consent. Patients discontinuing study treatment will enter the Long-term Follow-up Phase and remain on study until death, loss of follow-up, or withdrawal of consent, whichever comes first.

With an estimated accrual duration of 24 months, it is assumed that patients are expected to be followed for a minimum of approximately 9 months beyond Last Patient In (LPI) for the primary endpoint of MFS, to approximately 41 months beyond LPI for the key secondary endpoint of OS. This corresponds to total projected study duration of approximately 65 months.

If the study is not terminated beforehand per the recommendation of the IDMC, the end of trial in all participating countries will be defined as the time at which the secondary endpoint of OS has been met.

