7.6 SAFETY ANALYSES

7.6.1 Adverse Events

Patients will be assessed for adverse events at each monthly clinic visit while on the study. Adverse events (AEs) will be graded according to the NCI Common Terminology Criteria for Adverse Events (CTCAE) Version 4.0 and coded to preferred term and system organ class (SOC) using the most recent version of MedDRA.

All AEs reported during the AE reporting period (inclusive of the 28-day post last dose of study drug period) will be considered as treatment-emergent adverse events and will be summarized by treatment group as treated using all patients in the SAFETY population.

For each treatment group, adverse event incidence rates will be summarized with frequency and percentage by MedDRA SOC and preferred term, with all patients treated in that treatment group as the denominator, unless otherwise specified. In addition, AE incidence rates will also be summarized by severity and relationship to study drug. Treatment-related AEs are those judged by the Investigator to be at least possibly related to the blinded study drug. Patients with multiple occurrences of events will only be counted once at the maximum severity to study drug for each preferred team, SOC, and overall. Deaths that occur within 28 days after the last dose of study drug are defined as on-study deaths.

Summary tables of the following AEs will be provided:

ARN-509-003	
Statistical Analysis Plan v7.0 26 June 20	17

Page 17 of 34

- Overall summary of AEs: the number and percentage of patients who experienced any AE, any serious adverse event (SAE), any treatment-related AE, any treatment-related SAE, any discontinuations due to an AE, and any deaths
- All AEs by SOC and preferred term
- All AEs by SOC, preferred term, and toxicity grade
- All AEs by decreasing frequency of preferred term
- Grades 3 or 4 AEs by SOC, preferred term and toxicity grade
- Drug-related AEs by SOC and preferred term
- Drug-related AEs by SOC, preferred term, and toxicity grade
- Drug-related Grades 3 or 4 AEs by SOC, preferred term and toxicity grade
- AEs that led to study drug discontinuation by SOC and preferred term. Study drug discontinuation will be determined from the End of Treatment CRF (where reason for termination is "Adverse Event") and the specific AE will be determined from the AE CRF page (where action taken is "Withdrawn from Study")
- AEs that led to study drug discontinuation by SOC, preferred term, and toxicity grade.

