9.2 APPENDIX 2: TABLE SHELL FOR OVERALL SUMMARY OF ADVERSE EVENTS BY FORMULATION

	Placebo					
	Capsule	Tablet	Capsule+Tablet	Capsule	Tablet	Capsule+Tablet
Analysis Set: Safety population	###	###	###	###	###	###
Number of subjects with AEs	### (xx x%)	### (xx x%)	### (xx x%)	### (xx x%)	### (xx x%)	### (xx x%)
Drug-related ^a	### (xx x%)	### (xx x%)	### (xx x%)	### (xx x%)	### (xx x%)	### (xx x%)
Number of subjects with grade 3-4 AEs	### (xx x%)	### (xx x%)	### (xx x%)	### (xx x%)	### (xx x%)	### (xx x%)
Drug-related ^a	### (xx x%)	### (xx x%)	### (xx x%)	### (xx x%)	### (xx x%)	### (xx x%)
Number of subjects with SAEs	### (xx x%)	### (xx x%)	### (xx x%)	### (xx x%)	### (xx x%)	### (xx x%)
Drug-related ^a	### (xx x%)	### (xx x%)	### (xx x%)	### (xx x%)	### (xx x%)	### (xx x%)
Grade 3-4	### (xx x%)	### (xx x%)	### (xx x%)	### (xx x%)	### (xx x%)	### (xx x%)
Number of subjects with AEs leading to treatment discontinuation	### (xx x%)	### (xx x%)	### (xx x%)	### (xx x%)	### (xx x%)	### (xx x%)
Drug-related ^a	### (xx x%)	### (xx x%)	### (xx x%)	### (xx x%)	### (xx x%)	### (xx x%)
Number of subjects with AEs leading to death	### (XX X70)	### (XX X/0)	### (XX X/0)	### (XX X/0)	$\frac{1}{1}$	### (XX X/0)
Drug-related	$\frac{1}{10000000000000000000000000000000000$	$\frac{1}{1}$ (XX X/0)	### (XX X/6)	$\frac{1}{10000000000000000000000000000000000$	### (XX X/0)	### (XX X/0)
All deaths within 28 days of last dose	$\frac{1}{1}$	### (xx x%)	$\frac{1}{1}$ (XX X/6)	$\frac{1}{1}$ (xx x%)	$\frac{1}{1}$ (xx x%)	$\frac{1}{1}$
Adverse event	### (xx x%)	### (xx x%)	### (xx x%)	### (xx x%)	### (xx x%)	### (xx x%)
Death due to prostate cancer	### (xx x%)	### (xx x%)	### (xx x%)	### (xx x%)	### (xx x%)	### (xx x%)
other	(XX X/0)	(AA A/0)	······ (AA A/0)	(AA A/0)	(AA A/0)	(AA A/0)

^a Adverse events reported as related.

Note: Percent is based on the Safety population

Note: Treatment-emergent adverse events are those that occurred between the date of 1st dose of study drug and date of last dose of study drug+28 days. For each category, subjects are counted only once, even if they experienced multiple events in that category

٦

Г

ARN-509-003	
Statistical Analysis Plan v7.0 26 June 2017	Page 29 of 34

9.3 APPENDIX 3: MODIFIED MEDDRA QUERIES AS SEARCH CRITERIA FOR AE OF SPECIAL INTEREST

The search criteria for adverse events of special interest are based on adverse event preferred terms from MedDRA version 19.1 dictionary.

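### SAP 7.6.1 picks the AE behind a study drug discontinuation by a study-withdrawal label, so the by-term discontinuation tables may under-report drug-stopping AEs

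*SAP*

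**What the plan says.** SAP 7.6.1 lists two tables of AEs that led to study drug discontinuation: one by system organ class and preferred term, and one that adds toxicity grade. It also asks for a patient listing of the same events. The derivation rule is given once, under the first table, and names two forms for two purposes.

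- Who stopped: "Study drug discontinuation will be determined from the End of Treatment CRF (where reason for termination is 'Adverse Event".
- Which event caused it: "the specific AE will be determined from the AE CRF page (where action taken is 'Withdrawn from Study".

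The protocol keeps the two acts apart. Section 10 states: "If a patient's study treatment must be discontinued, this will not result in automatic withdrawal of the patient from the study". It adds: "All patients discontinuing study treatment will enter the Long-term Follow-up Phase". Section 15.6 repeats the point: "Patients discontinuing study treatment will enter the Long-term Follow-up Phase and remain on study until death, loss of follow-up, or withdrawal of consent".

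The by-formulation shell in SAP Appendix 2 has a row titled "Number of subjects with AEs leading to treatment discontinuation". No source is given for it.

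**The concern.** The tables are meant to show which toxicities end treatment. The stated filter asks instead which AEs ended study participation. Take a patient who stops drug because of an AE and then continues in follow-up with scans every 16 weeks, as Protocol 8.9 requires if metastasis has not been documented. That patient has stopped treatment but has not been withdrawn from the study. A site that reads the label at face value would have no reason to choose it for that AE. The patient would count as an AE discontinuation on the End of Treatment form but would contribute no preferred term to the tables.

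At stake is the breakdown by event of a main tolerability measure. SAP 7.6.1 also gives no rule for an End of Treatment record with reason 'Adverse Event' that has no matching AE, or for the reverse. Two outputs on the same subject would come from two forms with no stated check that they agree.

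**Working it through.** The plan states no figure here to reproduce, and no alpha, power or event count is involved. The check sets the passages side by side.

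**1. What the table counts.** By its title in SAP 7.6.1, AEs that led to discontinuation of study drug.

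**2. What the filter selects.** AEs whose action taken is the value 'Withdrawn from Study'. The SAP puts the value in quotation marks, so it reads as a data value to program against.

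**3. Whether the two coincide under the protocol.** They do not. By Section 10, stopping drug does not by itself withdraw the patient. By Section 15.6, a patient who stops drug remains on study until death, loss to follow-up or withdrawal of consent. Section 10 also has its own phrase for an AE-driven stop, and it refers to treatment: "If a patient is withdrawn from treatment due to an adverse event, the patient will be followed until the adverse event has resolved or stabilized".

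**4. What the label might mean on the CRF.** The documents do not contain the AE CRF. There are two possibilities.

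- The form has a separate option for study drug permanently discontinued. The SAP then names the wrong value, and AEs recorded under the right option drop out of the tables.
- 'Withdrawn from Study' is the only option for drug withdrawal. The SAP then names the intended value, but its plain meaning conflicts with the protocol, and sites may use it differently.

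**5. Size.** Let N be the number of AE-driven drug stops and c the share whose AE record carries 'Withdrawn from Study'.

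- Shown by preferred term: c × N
- Lost: (1 − c) × N

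If the label means drug withdrawn and is always used that way, c = 1 and nothing is lost. If the label is read literally and every such patient stays on study, c = 0 and everything is lost. The documents give no value between these limits. The End of Treatment count of patients does not involve c.

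**6. Outputs exposed.** The first by-term table carries the rule directly. The by-grade table and the listing have the same title and no rule of their own, so the natural reading is that they inherit it. The Appendix 2 row may or may not.

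**The case against.** The strongest reply is that the label is only loose wording. The documents do use 'study' where treatment is meant. Protocol 5.3.5 says that dose interruptions and reductions are "permitted provided that study discontinuation criteria have not been met (please see Section 10"; the section it points to lists reasons for ending treatment. Protocol 9.1.1 puts discontinuation from the study alongside a change in study dosing. The SAP sentence itself uses the label to find AEs behind drug discontinuation, so its intent is plain. If the CRF uses the label in that sense, nothing is lost.

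The reply also notes how much is protected. Patient-level counts come from the End of Treatment form. SAP 7.3 summarises reasons for treatment discontinuation by group. SAP 7.6.1 requires a narrative for each patient who discontinues drug because of an AE. A shortfall in the by-term tables would show up against those counts.

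Most of this stands. It removes any claim that events are certainly missed and confines the problem to the by-term tables and the listing. It does not remove the mismatch between the stated rule and the protocol, and it supplies no reconciliation.

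A reader might go further in two ways that the documents do not support.

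- **A numerical loss.** The protocol reports that 8 of 51 Phase II NM-CRPC patients discontinued because of AEs. Then 8/51 = 15.7%, and 0.157 × 800 is about 125 apalutamide patients. Turning that into events lost needs a value of c, which the documents do not give. The Phase II text also speaks of discontinuing the study, which is the same looseness that is in question here.
- **Apalutamide would look better tolerated.** That needs c to be below 1 and a known pattern of c and of true rates across arms. None of these is in the documents. The comparison of patients stopping drug for an AE does not depend on the label.

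**Conclusion.** The point holds as a defect in a stated derivation rule. SAP 7.6.1 names a study-withdrawal value to identify AEs that stopped the drug, while the protocol separates the two acts and keeps these patients on study. Applied literally, the two by-term tables and the matching listing may under-report drug-stopping AEs.

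The extent runs from none to all and depends on the AE CRF options and how sites used them. The conclusion assumes that the quoted label is the value to be programmed and that the by-grade table and listing follow the rule given for the first table. Whether the Appendix 2 row is affected is open, because its source is not stated.

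The effect is limited to safety tabulation. The correction is still worth making, because it costs little and protects an output that readers use to judge tolerability.

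**What to change.** In SAP 7.6.1:

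- Select AEs whose action taken with study drug is permanent discontinuation, regardless of study status, and cite the exact CRF value.
- Match every End of Treatment record with reason 'Adverse Event' to at least one such AE, and every such AE to an End of Treatment record with that reason. List mismatches and query them before database lock. The reverse match would also bring up AE-driven stops that were coded under another reason.
- If 'Withdrawn from Study' is the CRF's only label for drug withdrawal, say so in the SAP and rely on the reconciliation.
- State that the by-grade table, the listing and the Appendix 2 row use the same rule.

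The cost is a few lines of SAP text, a programming change and one reconciliation listing. No new data are needed beyond answers to queries, and no efficacy analysis changes.

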7.6.2 Laboratory Abnormalities

Only data collected by the central laboratory will be summarized. Local laboratory data collected for the purposes of planning treatment administration, dose modification, or monitoring adverse events, will not be summarized.

Normal ranges will be used to identify values that are outside the normal ranges and abnormal laboratory results will be graded according to the NCI CTCAE Version 4.0.

Descriptive statistics will be provided for selected test results and for the change from baseline by visit.

ARN-509-003 Statistical Analysis Plan v7.0 26 June 2017

Page 18 of 34

A shift summary of baseline grade by maximum post-baseline CTCAE grade will be presented, as appropriate. For each laboratory parameter, the baseline laboratory value will be defined as the last laboratory value collected on or prior to the date of the first dose of study drug. Patients who develop toxicities of Grade \geq 3 will be listed.

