In the NM-CRPC subgroup (n =51 ), the most frequent treatment-related adverse events reported in  $>10\%$  as of 30 November 2013 are fatigue (43%), diarrhea (31%), nausea (20%), increased thyroid stimulating hormone (12%), dysgeusia (12%), and hot flush 12%. Eight (16%) patients have discontinued the study due to adverse events. Seven (14%) patients have discontinued due to disease progression. No deaths were reported in this subgroup as of the safety cutoff.

Refer to the Investigator's Brochure for most up to date information.

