#### **8.5 EVERY 16 WEEKS STARTING FROM CYCLE 1 DAY 1 (±2 DAYS)**

- Collect blood for TSH, fasting lipid panel, and testosterone
- If TSH is abnormal; total T3, free T4 (direct), and total T4 are required

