### **13.3.2 Analysis of Clinical Laboratory Results**

Only data collected by the central laboratory will be summarized. Local laboratory data collected for the purposes of planning treatment administration, dose modification, or monitoring adverse events, will not be summarized.

Normal ranges will be used to identify values that are outside the normal ranges and abnormal laboratory results will be graded according to the NCI CTCAE Version 4.0. Descriptive statistics will be provided for each test result and for the change from baseline by visit.

A shift summary of baseline grade by maximum post-baseline CTCAE grade will be presented, as appropriate. For each laboratory parameter, the baseline laboratory value will be defined as the last laboratory value collected on or prior to the first dose of study drug.

Patients who develop toxicities of Grade  $\geq 3$  will be summarized. Laboratory test results not having CTCAE grade will also be summarized. Parameters that have criteria available for both low and high values (e.g., hypercalcaemia vs. hypocalcaemia) will be summarized for both criteria. Patients will only be counted once for each criterion.

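### SAP 7.6.2 is narrower than Protocol 13.3.2 on laboratory data: unnamed selected tests, Grade ≥3 values listed rather than summarized, and no guaranteed table for results without a CTCAE grade

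*SAP*

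**What the plan says.** Protocol 13.3.2 (Analysis of Clinical Laboratory Results) makes four commitments that matter here.

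- On scope: "Descriptive statistics will be provided for each test result and for the change from baseline by visit".
- On patients who reach Grade 3 or higher, and on ungraded tests: these "will be summarized. Laboratory test results not having CTCAE grade will also be summarized".
- On direction: "Parameters that have criteria available for both low and high values (e.g., hypercalcaemia vs. hypocalcaemia) will be summarized for both criteria".

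SAP 7.6.2 (Laboratory Abnormalities) covers the same ground in much the same order, but reads differently. On scope: "Descriptive statistics will be provided for selected test results and for the change from baseline by visit". Patients who reach Grade 3 or higher "will be listed". It has no sentence on ungraded results and none on low and high criteria. Both documents plan a shift table from baseline grade to worst post-baseline CTCAE grade, where appropriate.

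On data collection, Protocol 8.5 has a 16-weekly instruction: "Collect blood for TSH, fasting lipid panel, and testosterone". It adds total T3, free T4 and total T4 whenever TSH is abnormal. Protocol 1.1.3 gives increased TSH as a treatment-related AE in 12% of the Phase II NM-CRPC subgroup (n = 51). SAP 2.2 lists the incidence of laboratory abnormalities among the trial's other evaluations.

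**The concern.** The SAP is the document from which the tables are programmed, and Protocol section 13 defers to it for detailed methodology. Where it restates a protocol section in narrower terms, the narrower set is likely to be what is produced. SAP section 1 promises to report deviations from the SAP. A report that followed SAP 7.6.2 to the letter would not be such a deviation, so the shortfall against the protocol need not be disclosed.

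The part most exposed is any central-laboratory test that carries no CTCAE grade. Such a test cannot enter a grade-shift table, and its by-visit statistics depend on its being among the selected tests. Thyroid tests and lipids are the natural examples. Raised TSH is a treatment-related AE reported in 12% of the Phase II NM-CRPC subgroup, and Protocol 1.1.2 describes cholesterol increases in rats and dogs that it attributes to anti-androgen activity. Central values are scheduled every 16 weeks for about 1,200 men, yet no SAP sentence commits to tabulating them.

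A listing of Grade ≥3 values gives no rate and no comparison between arms, so taken alone it does not deliver the incidence that SAP 2.2 names.

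**Working it through.** There is no sample size, power or alpha figure to reproduce. The check is a comparison of the two sections.

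| Output | Protocol 13.3.2 | SAP 7.6.2 | Relation |
|---|---|---|---|
| By-visit descriptive statistics | Every test | Selected tests, no list or rule | Conflict |
| Grade ≥3 patients | Summarized | Listed | Conflict |
| Results without a CTCAE grade | Summarized | Not mentioned | Silence |
| Low and high criteria | Summarized for both | Not mentioned | Silence |
| Grade-shift table | Where appropriate | Where appropriate | Same |

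The count is two conflicts, two silences and one agreement.

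**Could listed be shorthand for summarized?** No. SAP 7.6.3 says marked vital-sign abnormalities are both summarized and listed, and SAP 7.6.1 gives its summary tables and its patient listings separately. The SAP uses the two words for different outputs.

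**Is the difference explained?** No. The summary of major changes at the end of the SAP records even a revision of the vital-sign cut-offs in 7.6.3, but has no entry for laboratory analyses. It compares SAP versions with one another, so it would not show wording that had been in the SAP from the start. Either way, no reason is on record.

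**Which routes to a table remain for a given test?**
1. It is among the selected tests. This is discretionary, because the selection is not stated.
2. It has a CTCAE grade and the shift table is judged appropriate. The documents do not reproduce CTCAE, so whether TSH, T3/T4 or each lipid measure has a grade cannot be settled from them.

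A test that fails both conditions has no planned laboratory table in the SAP. The protocol's ungraded-results sentence, "Laboratory test results not having CTCAE grade will also be summarized", closes exactly this gap.

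**Do the AE tables cover TSH?** In part. SAP 7.6.1 tabulates AEs by preferred term for each treatment group, and SAP Appendix 3 includes increased TSH among the thyroid terms of special interest. Protocol 9.1.1 makes a laboratory finding reportable as an AE on stated conditions, one being that it leads to further diagnostic testing. Because an abnormal TSH triggers reflex T3/T4, it arguably meets that condition. But reporting still passes through the investigator. SAP 7.6.1 also names no summary table for the special-interest categories, only narratives for Grade 3 or higher. The AE tables therefore cover reported events, not the measured values.

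**What does the 12% measure?** 6/51 = 11.8%, which rounds to 12% (5/51 = 9.8%; 7/51 = 13.7%). The exact 95% interval for 6/51 is 4.4% to 23.9%. This is an investigator-attributed AE rate, not a laboratory rate. It shows why the test matters but does not measure the gap.

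**The case against.** The strongest reply is that SAP section 1 describes the plan as supplementing the protocol, so Protocol 13.3.2 remains in force and silence cancels nothing. That is right for the ungraded-results and low/high summaries, which the SAP omits without revoking. It does not answer the other two items, where the SAP addresses the same output and states something narrower.

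Three stronger conclusions might be inferred, and the documents do not support them.

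- *That measured TSH will go untabulated.* This needs TSH to be both ungraded and unselected, and neither is shown. Nor would a TSH rise go unreported, because increases reported as AEs appear by treatment group. Scaling the 12% to the apalutamide arm as a count of men lost from view would also be wrong, since it is a rate of reported AEs, and men with such AEs are the ones the AE tables already include.
- *That Grade ≥3 counts disappear.* A shift table, if produced, carries them in its Grade 3 and higher columns. It is promised only where appropriate, so this reduces the problem without removing it.
- *That opposite abnormalities will be pooled.* The SAP does not say so. It only omits the protocol's assurance that they will be separated.

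Two further cautions stand. Neither laboratory section states presentation by treatment group, so the SAP did not remove it. And raised TSH should be described as a treatment-related AE reported in a Phase II subgroup of 51 men, not as an established drug effect.

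**Conclusion.** The concern holds as an inconsistency between the two documents. SAP 7.6.2 contradicts Protocol 13.3.2 on two laboratory outputs and is silent on two more, with no recorded reason. The consequence that can be stated firmly is that a central-laboratory test without a CTCAE grade has no guaranteed table in the SAP. TSH, reflex T3/T4 and lipids may be among these tests; that depends on grading and selection that the documents do not disclose.

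The size is modest. No efficacy inference is affected, the data are collected and remain available, and AE tables together with a possible grade-shift table give partial cover. The point is still worth acting on, because the SAP narrows the sponsor's own protocol on a safety evaluation that the SAP itself lists, and bringing it back into line costs very little.

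**What to change.** Align SAP 7.6.2 with Protocol 13.3.2:

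1. Extend the by-visit descriptive statistics from selected tests to each test result.
2. Restore the summary of results without a CTCAE grade.
3. Restore the separate summaries for low and high criteria.
4. State that Grade ≥3 values will be summarized by treatment group as well as listed.
5. For tests without a CTCAE grade, including TSH if it is ungraded, tabulate shifts against the normal range by treatment group.

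Item 5 and the words on treatment group go slightly beyond the protocol, which asks for a summary without giving its form. They make the restored commitment specific enough to program. If a restricted set of tests is really intended, the SAP should name them and record the departure from the protocol with a reason.

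The cost is a short SAP edit and a few more tables. No new assessment is needed, and no treatment or patient-management rule changes.
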